1. PREVIOUS STUDY HISTORY

Has this study ever been reviewed and rejected/disapproved by another IRB prior to submission to this IRB?

No Yes – if yes, please explain:

2. BRIEF SUMMARY OF RESEARCH

- *The summary should be written in language intelligible to a moderately educated, non-scientific layperson.*
- *It should contain a clear statement of the rationale and hypothesis of your study, a concise description of the methodology, with an emphasis on what will happen to the subjects, and a discussion of the results.*
- *This section should be ½ page*

Stroke is the fifth leading cause of death and the leading cause of serious long-term disability in the U.S. [1]. Post-stroke impairment is often characterized by hemiparesis or weakness of the upper and lower limbs, rendering the individual dependent for most activities of daily living. Traditional stroke rehabilitation medicine consists of a combination of one-on-one treatment and group therapy with physical, occupational and speech therapists, focusing on both labor-intensive motor training of the affected limbs, as well as compensatory training of the unaffected side of the body. Even with aggressive standard rehabilitation, 65 percent of patients cannot incorporate their affected hand in functional activities six months after stroke, and only 25 percent of patients return to the level of life participation equivalent to that of community-matched healthy controls [2].

We have previously demonstrated that robotic therapy provides functionally and clinically significant benefits to upper limb motor recovery after stroke, and has been consequently acknowledged by the American Heart Association as an effective form of stroke rehabilitation [3-5]. Robotic intervention operates through a series of interactive motors with low impedance which move a patient's limb when the patient cannot move and progressively intervene less as the patient improves. The advantage of this technology is to deliver reproducible movement without tiring, increasing the level of training intensity and potentially decreasing the level of impairment. Though the clinical benefit of robotic interventions to reduce motor impairment after stroke is well established, the results are generally not curative.

Promising new animal research suggests that vagus nerve stimulation paired with motor intervention induces movement-specific plasticity in the motor cortex and improves limb function after stroke [6-7]. These results were recently extended to the first clinical trial, in which patients with stroke demonstrated significant improvements in upper limb function following rehabilitation paired with implanted

VNS [8]. Currently, vagus nerve stimulation is being used clinically to treat a number of human diseases including migraine headaches, epilepsy, and depression [9-11]. Many of these treatments are non-invasive, activating the auricular branch of the vagus nerve transcutaneously through the cymba concha at the pinna of the ear [9-10, 23, 40]. We propose here a pilot study combining non-invasive stimulation of the vagus nerve with upper limb robotic therapy to investigate the potential of tVNS to augment improvements gained with robotic therapy in patients with chronic hemiparesis after stroke.

3. INTRODUCTION/BACKGROUND MATERIAL/PRELIMINARY STUDIES AND SIGNIFICANCE

- *Describe and provide the results of previous work by yourself or others, including animal studies, laboratory studies, pilot studies, pre-clinical and/or clinical studies involving the compound or device to be studied.*
- *Include information as to why you are conducting the study and how the study differs from what has been previously researched, including what the knowledge gaps are.*
- *Describe the importance of the knowledge expected to result*

Vagus nerve stimulation (VNS) is an FDA approved form of therapy to treat refractory epilepsy, depression, and cluster headaches. Because VNS is believed to drive activation of neuromodulatory nuclei associated with plasticity (e.g. cholinergic basal forebrain and noradrenergic locus coeruleus), it has also been recently investigated for use in the treatment of neurological diseases and injuries. Animal models of tinnitus, ischemic stroke, intracerebral hemorrhage, and traumatic brain injury benefitted from repetitive bursts of VNS during rehabilitative interventions [12-15]. Khondaparast et al (2013) reported that VNS paired with intensive forelimb motor rehabilitation improved force generation recovery in rats with chronic motor impairment following ischemic infarction of the primary motor cortex. Specifically, rats who received VNS during motor rehabilitation tasks improved twice as much as those who received rehabilitation alone, and returned to near pre-lesion levels of motor performance [7]. These results were also replicated in animal models of cerebral hemorrhage and TBI [12-13]. Taken together, these pre-clinical studies suggest VNS may be a viable additive rehabilitation intervention to deliver greater functional outcomes following neurological injury.

However, these previous rehabilitation trials have shown that such improvements are often selective only to the task which has been paired with VNS. Specifically, in rats, motor behaviors paired with implanted VNS following stroke demonstrated selective increases in the size of the motor representations within the motor cortex for trained behaviors, while motor representations for untrained tasks or tasks performed without VNS remained relatively unchanged [19]. Human and animal models of tinnitus rehabilitation involving selective pairing of VNS with tones outside of the tinnitus white noise perceptual range resulted in significant reductions in the perception of tinnitus for up to three months [20-21]. In stroke rehabilitation, one of the most notable hindrances to motor recovery is the persistence of

maladaptive upper and lower limb flexor synergy patterns. Upper extremity flexor synergy is characterized by a fixed pattern of scapular retraction, shoulder abduction/external rotation, elbow/wrist/finger flexion, and wrist supination, resulting a 'curling in' of the arm towards the body with a rigid, closed hand. It is caused by damage to the corticospinal tract (CST), and subsequent upregulation of interneuron spinal networks and other descending spinal pathways, ultimately resulting in movement limitations, which are greatest for extensor movements [22]. Given the apparent task-selectivity of VNS training, current delivered only during extensor movements of a motor therapy task might lead to more efficient recovery of arm function after stroke.

Preliminary clinical evidence suggests that implanted VNS augments the benefits of upper limb rehabilitation for individuals with chronic upper limb hemiparesis post-stroke. Dawson et al (2015) randomized twenty-one patients who were greater than 6 months from an ischemic stroke to receive either VNS plus rehabilitation (N=9) or upper limb rehabilitation alone (N=11). Rehabilitation intervention was intensity matched across groups, and consisted of three 2hr treatment sessions per week for 6 weeks. VNS was delivered manually by the therapist via button press while the patient completed all prescribed motor tasks. Results from the per-protocol analysis demonstrated a significant improvement in upper limb Fugl Meyer scores for the VNS plus rehabilitation group as compared with the rehabilitation group alone (between group difference= 6.5 points). There were no serious adverse device effects, though side effects included transient dysphagia and vocal fold paralysis following implantation, and temporary nausea and taste disturbances following stimulation [8]. Overall, this first clinical trial of stimulator implanted VNS suggests a promising augmentative tool may become available to enhance post-stroke motor rehabilitation. However, given that vagus nerve stimulation appears to be task-selective and dose-sensitive, refinement of stimulation parameters is still needed. Thus, we propose an investigation of specific vagus nerve stimulation timing parameters via a transcutaneous route to potentially improve intervention efficacy and decrease side effects.

For this study, investigators in the Laboratory of Rehabilitation Robotics are collaborating with investigators in the Center for Bioelectronic Medicine (CBEM) to test the hypothesis that vagus nerve stimulation via an external electrode placed on the ear and timed to deliver stimulation during upper limb extensor movements will improve the outcome in patients after stroke. Currently, CBEM investigators have experience with 8 healthy controls and 8 patients with lupus delivering transcutaneous auricular vagus nerve stimulation (tVNS) without any serious adverse events. The advantages of non-invasive tVNS device for use in stroke rehabilitation are to eliminate the need for surgical implantation, reducing untoward side effects in an already vulnerable population, and to potentially develop a clinical tool for better and more efficient functional recovery.

In our previous research, the Laboratory for Rehabilitation Robotics employed robotic devices to train movement in paralyzed limbs with well over 300 patients, and have established robotic intervention as a recommended standard of care [3]. We have demonstrated that robotic interventions alone provide safe, targeted, impairment altering upper and lower limb motor rehabilitation in the chronic phase of stroke recovery [3-5]. We have subsequently investigated the combination of robotic training with two bioelectronic interventions, transcranial direct current stimulation (tDCS) and trans-spinal direct current stimulation (tsDCS), and specifically examined the optimal timing parameters for administration of non-invasive brain and spinal stimulation devices during upper limb recovery. To that end, we demonstrated that tDCS improves robotic kinematic scores in patients with post-stroke hemiparesis, but only when it is used prior to robotic training, and not when applied during or after robotic therapy [14]. These results suggest tDCS increases cortical excitability and neural plasticity for a time period, and that robotic therapy is more effective when applied at that time. In another group of experiments, we are testing the efficacy of tsDCS in order to pair it with robotic intervention. We have demonstrated that tsDCS significantly reduces both objective measures of the spastic catch response (e.g. changes in peak amplitudes measured with force transducer and EMG) as well as clinical measures (Tardieu/MAS) of upper extremity spasticity in twenty-one patients in the chronic phase after stroke. Importantly, these improvements are seen immediately following 5 days of stimulation compared to the sham condition, and are maintained for three weeks or greater. While these studies have been crucial in characterizing optimal treatment windows and sensitively measuring kinematic profiles of motor recovery, the stimulation interventions were delivered in an “open loop,” which is to say the stimulation was not interactively timed with a motor task. Recent evidence suggests that delivery of closed loop stimulation, in which stimulation is provided precisely online during a motor therapy task, may yield greater recovery of function [16-18]. However, better understanding of task-selectivity and the timing of tVNS stimulation parameters is still needed.

Our experience treating patients in post-stroke condition, and with robotics combined with non-invasive stimulation, and also with tVNS will facilitate the experiment we propose. Specifically, we will deliver tVNS in a closed loop approach during only extensor movements for consecutive upper limb robotic therapy training sessions in order to test whether task-specific closed loop tVNS combined with upper limb robotic intervention can significantly improve arm function compared to a sham condition.

4. OBJECTIVE(S)/SPECIFIC AIMS AND HYPOTHESES

- *A concise statement of the goal(s) of the current study.*
- *The rationale for and specific objectives of the study.*
- *The goals and the hypothesis to be tested should be stated.*

Specific Aim 1: To evaluate whether 3 weeks of robotic therapy paired with tVNS delivered only during extensor movements will significantly change

EMG activation patterns of up the upper extremity during unassisted gravity-eliminated movements in approximately 18 patients with chronic post-stroke hemiparesis compared to sham condition.

In patients with chronic upper-limb hemiparesis post-stroke, we will use a within-subjects repeated measure design to determine if 9 sessions of active tVNS during only extensor movements significantly alters EMG activation of the biceps brachii and triceps as compared to a sham condition.

Specific Aim 2: To determine whether 3 weeks of robotic therapy paired with tVNS will significantly improve clinical measures of upper extremity motor function in approximately 18 patients with chronic hemiparesis after stroke compared to a sham condition.

We will use a within-subjects repeated measures design to determine if 9 sessions of robotic therapy paired with active tVNS during only extensor movements significantly improves upper extremity motor function in patients with chronic post-stroke hemiparesis as compared to sham tVNS paired with robotic therapy.

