5. RESOURCES AVAILABLE TO CONDUCT THE HUMAN RESEARCH

- *Explain the feasibility of meeting recruitment goals of this project and demonstrate a potential for recruiting the required number of suitable subjects within the agreed recruitment period*
 - *How many potential subjects do you have access to?*
- *Describe your process to ensure that all persons assisting with the trial are adequately informed about the protocol and their trial related duties and functions*

The study will involve approximately 36 subjects with chronic hemiparesis following stroke. The research team will be led by [name], who has extensive experience recruiting for clinical trials related to stroke. Additionally, the Northwell Health System treats over 1000 patients with stroke annually, and provides an excellent recruitment population eligible for participation in this study.

The team in the Laboratory of Rehabilitation Robotics has substantial experience in the field of stroke rehabilitation. [name] is a treating neurologist, investigator, and lecturer with over 30 years of clinical and research experience with neurological recovery. [name] is a Physiatrist and Research Coordinator with over ten years of clinical experience in the treatment of neurological injuries and neurodegenerative impairment. [name] is a Research Coordinator and Speech-Language Pathologist with extensive clinical and research experience related to neurological injury. [name] is a Research Assistant with a background in neuroscience, and an expertise in EMG spike analysis.

Additionally, the team in the Center for Bioelectronic Medicine has extensive experience in engineering, programming, and clinical administration of vagus

nerve stimulation via tVNS devices. The team has developed a wireless all-in-one tVNS stimulator, the device was co-designed with an ISO 13485 certified company (MIDI), and fabricated by MIDI, and supplied to the CBEM team.

In order to ensure everyone assisting on the study is well versed in the protocol requirements, there will be a study team meeting after institutional approval is obtained. At this meeting, everyone will be reminded of the study design and all of the study processes. In addition, there will be a delegation of responsibility log created to outline the specific tasks of each study member during the course of the study. The study team will also routinely meet to discuss study progress and address any questions that arise.

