8. NUMBER OF SUBJECTS

- *Indicate the total number of subjects to be accrued locally. If applicable, distinguish between the number of subjects who are expected to be pre-screened, enrolled (consent obtained), randomized and complete the research procedures.*
- *If your study includes different cohorts, include the total number of subjects in each cohort.*
- *If this is multisite study, include total number of subjects across all sites.*

This is a double-blind, sham-controlled pilot study. The total target enrollment is 36 subjects with post-stroke hemiparesis. Only patients who meet inclusion criteria following screening will be enrolled. We have anticipated a 10-15% drop-out rate in determining target enrollment.

This study will use a randomized controlled study design to determine whether nine repeated treatments of upper extremity robotic therapy paired with tVNS delivered only during extensor movements significantly changes objective EMG activation patterns and significantly improves clinical measures of upper extremity motor function in patients with chronic post-stroke hemiparesis as compared to a sham condition.

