11. RESEARCH PROCEDURES

- *Include a detailed description of all procedures to be performed on the research subject and the schedule for each procedure.*
- *Include any screening procedures for eligibility and/or baseline diagnostic tests*
- *Include procedures being performed to monitor subjects for safety or minimize risks*
- *Include information about drug washout periods*
- *If drugs or biologics are being administered provide information on dosing and route of administration*
- *Clearly indicate which procedures are only being conducted for research purposes.*
- *If any specimens will be used for this research, explain whether they are being collected specifically for research purposes.*
- *Describe any source records that will be used to collect data about subjects*
- *Indicate the data to be collected, including long term follow-up*

Consecutive Sessions of tVNS during robotic therapy intervention

Thirty-six patients with chronic, post-stroke upper extremity hemiparesis will be accepted into this study, and randomized to receive either sham or active tVNS treatment coupled with robotic therapy. There will be 2-3 baseline measurement periods prior to treatment. Following the lead-in period, subjects will participate in a training period consisting of approximately 1 hour sessions robotic therapy paired with tVNS 3x/week for 3 weeks, for a total of 9 sessions. Following the training period, subjects will complete clinical and objective measures both immediately at discharge and again a 3-month follow-up visit.

Lead-in Period

- Week 1, Visit 1 (approximately 90 minutes)
 - Baseline clinical outcome measures
 - Instrumental measures with EMG
 - Medical screening
 - Consent
- Week 1, Visits 2-3 (approximately 60 minutes each)
 - Baseline clinical outcome measures
 - Instrumental measures with EMG

Training Period

- Weeks 2-4, Visits 4-12 (approximately 60 minutes)
 - robotic therapy + tVNS

- Device tolerance questionnaires (every session)

Discharge Evaluation

- Week 4, Visit 13 (approximately 60 minutes)
 - Clinical outcome measures
 - Instrumental measures with EMG

Follow-Up Evaluation

- Week 16, Visit 14 (approximately 60 minutes)
 - Clinical outcome measures
 - Instrumental measures with EMG

**Phase II
Schedule**

	Screen 1	Screen 2	Screen 3	taVNS Tx + robotics	DC eval	3 mo FU
	Visit 1	Visit 2	Visit 3	Visit 4-12	Visit 13	Visit 14
Informed Consent	X					
Medical Hx	X					
Demographic Info	X					
Inclusion Criteria	X					

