12. STATISTICAL ANALYSIS

- *Describe how your data will be used to test the hypotheses.*
- *State clearly what variables will be tested and what statistical tests will be used.*
- *Include sample size calculations.*
- *If this is a pilot study, state which variables will be examined for hypothesis generation in later studies.*

For our primary outcome measure, we will investigate whether tVNS paired in a closed loop with robotic therapy changes peak amplitude EMG activation in muscle groups along the shoulder and elbow. We hypothesize that upper extremity flexor synergy will be significantly improved when active tVNS is applied during extensor movements as compared to a sham condition, and will lead to an increase in EMG peak activation at the triceps brachii (elbow extensor muscle). This will be examined with a 2x3 ANOVA with condition (active stimulation vs. sham) and time (peak amplitude of EMG activation during extensor movements at admission, discharge, and follow-up) as factors.

For our secondary outcome measure, we will test whether active tVNS during extensor movements paired in a closed loop with intensive robotic intervention (9 sessions) significantly improves upper extremity motor function as compared to sham tVNS paired with intensity-matched robotics. This will be examined with a 2x3 Friedman ANOVA with condition (active vs. sham tVNS) and time (upper extremity fugl meyer score at admission, discharge, and 3 month FU) as factors.

Since this is a pilot study, there are presently no data from which we can derive a power calculation. However, we propose to enroll 36 subjects, in order to achieve a target of at least fifteen subjects per treatment group and also allow for a 10-15% drop out rate. In our extensive past experience with upper limb hemiparesis rehabilitation studies, 10-15 subjects per treatment group is required at minimum to capture a measurable treatment response. Additionally, two other early pilot studies investigating post-stroke upper limb motor rehabilitation combined with VNS found a significant improvement in motor performance with nine and fourteen subjects per treatment group (e.g. sham and active VNS), respectively [8 & 41].

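### The Aims label a parallel-group comparison as within-subjects, and the Friedman ANOVA named for the Fugl-Meyer score cannot compare the two arms

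*Combined protocol and SAP*

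**What the plan says.** Section 4 of the combined protocol and SAP gives the design for each Aim. For Aim 1, "we will use a within-subjects repeated measure design to determine if 9 sessions of active tVNS" alters EMG activation compared with sham. For Aim 2, "We will use a within-subjects repeated measures design to determine if 9 sessions of robotic therapy paired with active tVNS" improves motor function compared with sham. The patient numbers are "in approximately 18 patients with chronic post-stroke hemiparesis compared to sham condition" for Aim 1 and "in approximately 18 patients with chronic hemiparesis after stroke compared to a sham condition" for Aim 2. Neither Aim says whether 18 is a total or a per-arm figure.

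The operative sections describe a randomised parallel-group trial:

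- Section 5: "The study will involve approximately 36 subjects with chronic hemiparesis following stroke".
- Section 8: "This study will use a randomized controlled study design to determine whether nine repeated treatments" changes EMG and improves motor function relative to sham. The enrolment target is 36.
- Section 11, Research Procedures: "Thirty-six patients with chronic, post-stroke upper extremity hemiparesis will be accepted into this study, and randomized to receive either sham or active tVNS". The schedule has a single training period of nine sessions, then a discharge visit and a 3-month follow-up.
- Section 11, Randomization and Blinding: patients are stratified by Fugl-Meyer score, assigned to one of two groups, and told that their chance of each is 50-50.
- Section 12: the target is no fewer than 15 patients in each treatment group, with 10-15% dropout allowed for.

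Section 12 analyses the primary outcome (EMG peak amplitude) by a 2x3 ANOVA with condition and time as factors. It does not say which factor is between-subject. For the secondary outcome, the upper-extremity Fugl-Meyer score: "This will be examined with a 2x3 Friedman ANOVA with condition (active vs. sham tVNS) and time".

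**The concern.** In both Aims, the within-subjects design is the stated means of comparing active with sham stimulation. That requires each patient to be observed under both conditions, and the trial does not do this. Section 12 does not correct the label: it lists condition and time as factors without assigning either to a level, and does not say which term of the model tests the hypothesis.

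For the Fugl-Meyer score the problem reaches the analysis itself. Friedman's test is a within-block rank test. If it is run on these data, what it can deliver is a test of change over time, within each arm or with the arms pooled. Section 3 says that robotic therapy alone reduces impairment in chronic stroke, so improvement is expected in both arms. A significant time effect in the active arm would then say nothing about tVNS. Nor would a significant result in one arm beside a non-significant result in the other, because that is not a test of the difference between them.

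**Working it through.** **1. Is a within-patient active-versus-sham contrast available?** It needs at least one measurement per patient under each condition. Section 11 assigns each patient to one condition and schedules one nine-session block, with no second period or washout. The number of patients observed under both conditions is therefore zero. Condition varies between patients. Time (admission, discharge, follow-up) varies within patients.

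**2. Where does 18 come from?** The inputs are section 12's 15 per group and 10-15% dropout, with two equal arms inferred from the 50-50 chance in section 11.

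- Formula: patients per arm = 15 / (1 − dropout), rounded up.
- At 15% dropout: 15/0.85 = 17.6, so 18 per arm and 2 × 18 = 36 in total. This reproduces the plan's enrolment figure exactly.
- At 10% dropout: 15/0.90 = 16.7, so 17 per arm and 34 in total.
- Check in the other direction: 18 × 0.85 = 15.3 and 18 × 0.90 = 16.2 expected completers per arm, both above 15.

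The 18 in the Aims equals the per-arm number of the parallel design. What is missing is the words per arm.

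**3. What can Friedman's test do with these data?** Each patient supplies three Fugl-Meyer scores, which are ranked 1, 2 and 3 within that patient.

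- *Condition.* Every patient's ranks sum to 1 + 2 + 3 = 6 and average 2, whichever arm the patient is in. (Tied scores take average ranks and leave the sum unchanged.) Each arm's mean rank is therefore 2 by construction, and an overall difference between arms cannot appear.
- *Condition by time.* The statistic sums ranks over patients at each time point. It has a time effect and no between-group term. Two patients whose scores rise at each visit both receive ranks 1, 2, 3, even if one gains far more than the other. Running the test separately in each arm gives two tests of time and no test of the difference.
- *All six condition-by-time cells as one block.* This needs 2 × 3 = 6 scores per block, and a patient supplies only three. Filling the block would mean pairing an active patient with a sham patient. Section 11 stratifies randomisation in two Fugl-Meyer bands but creates no matched pairs.

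None of these routes tests active against sham.

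**4. Does the primary analysis have the same fault?** No. A 2x3 ANOVA can be run as a mixed design, with condition between patients and time within patients, and its interaction then compares change between arms. Section 12 needs to say so, but the named method is compatible with the trial.

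**The case against.** The strongest defence is that the operative sections agree with one another. Sections 5, 8, 11 and 12 all give 36 patients or two treatment groups, and section 8 restates both Aims under a randomised controlled design. The within-subjects wording may refer loosely to the repeated time points, which are indeed within-patient. An analyst working from section 11 would find no pairs to form. The trial is a pilot, and the Friedman problem concerns the secondary outcome and would remain even if the Aims were reworded.

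Most of this stands, and it rules out three stronger readings that a reader might infer:

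- *That the trial cannot test its hypotheses.* Both hypotheses concern active versus sham after nine sessions. Two randomised arms measured at admission, discharge and follow-up can test them, and section 12 frames them that way.
- *That 18 and 36 are rival total sample sizes.* The plan's own dropout arithmetic makes 18 the per-arm figure, and no operative section supports 18 as a total.
- *That the Aims overstate the trial's sensitivity.* The plan makes no power claim; section 12 says that no data are available for a power calculation and argues for its size per treatment group. Setting a paired design with 18 patients and no dropout against 15 completers per arm without baseline adjustment would also be an uneven comparison.

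The defence does not rescue the Friedman ANOVA. Its name might be meant loosely for some rank-based factorial analysis, but section 12 specifies none, and the test as named has no between-group factor.

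**Conclusion.** The point holds in two parts of unequal weight. The lesser part is labelling: both Aims call a between-patient comparison within-subjects and omit per arm after 18, while the rest of the document describes 36 patients in two parallel arms. The greater part is wrong as written: the Friedman ANOVA cannot test the condition effect or the condition-by-time interaction, so the Fugl-Meyer outcome, the sole measure in the secondary analysis, has no valid named test of active against sham.

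The size of the problem is one efficacy outcome without a usable test, plus an ambiguity in the primary analysis that a sentence would remove. No change in sample size follows. The conclusion rests on the current text of sections 4, 8, 11 and 12 and on Friedman's test in its ordinary sense. The per-arm reading of 18 also assumes equal allocation, which is inferred from the 50-50 statement.

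**What to change.** - **Section 4.** Reword both Aims as a randomised parallel-group comparison of active with sham tVNS, with repeated measures over time, in about 18 patients per arm (36 in total).
- **Section 12, both outcomes.** State that condition is a between-subject factor and time a within-subject factor, and that the between-arm difference in change (the condition-by-time term) tests each hypothesis. Name the post-treatment time point or points that the test uses. Section 12 lists discharge and the 3-month follow-up, and the choice between them is the sponsor's.
- **Section 12, Fugl-Meyer score.** Replace the Friedman ANOVA with a method that compares arms: baseline-adjusted ANCOVA, a mixed model with condition, time and their interaction, or, if a rank method is preferred, a rank test comparing change between arms.

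The cost is an amendment to the Aims wording and the analysis text. Replacing the Friedman test is a change of analysis and more than an edit, so it should be settled before outcome data are examined by arm. Enrolment, randomisation, visits and measurements stay as they are.
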